All staff with contact with study participants will be trained on how to recognize, assess, and intervene, in a manner appropriate to their training backgrounds, in the case of a psychiatric emergency. They will be trained and supervised by an on-site team member who is a licensed clinical psychologist (PI, Co-I, or site PI). Staff will be trained with direct instruction and role plays, using the structured protocol depicted in Figure 1. The protocol is described in further depth below. Training will take place prior to initiating contact with any potential participants and again on an as-needed basis for staff added to the project in the future.

All potential collaborators and study therapists on these research activities will have completed comprehensive training in the areas of research ethics, protection of human subjects, and suicide prevention. They will also have completed all VA required trainings pertinent to cyber security, VHA privacy policy (HIPAA), research data security and privacy, ethical principles of human subjects' protection, good clinical practice, and suicide prevention. In addition, [name] graduate coursework included a three-credit course on ethics.

We will utilize access to local and national mental health resources available through the VA, including the suicide prevention hotline, risk assessments through Mental Health during regular business hours (Psychiatry Urgent Care), or the facility's Emergency Room during off hours. In the unusual event of an on-site psychiatric emergency involving a participant who is not a Veteran, including threats of or acute risk for IPV, the participant will be triaged within VA facilities. If indicated based on psychiatric evaluation, non-Veterans will be transferred for appropriate care in community. Once stabilized, they will be eligible to enter or re-enter the study.

Suicide Management Protocol

Non-clinical study staff conduct screening and consenting with participants. Consequently, these staff should be prepared should a veteran or his/her support person express distress or thoughts indicating potential risk for a psychiatric emergency. Research staff's obligation is to minimize risk to participants by eliminating immediate danger (Wendler & Grady, 2000). Short, straight-forward, interview instruments are ideally suited for staff, with any training background, to take an algorithmic approach to participants who may pose an imminent danger to themselves and warrant emergency intervention.

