3. Have a SP (intimate partner, family member, or friend) with contact at least 3 times a week	Self-report item	8. Severe substance use problem in past 3 months	SCID-5-CT ¹²
4. Will allow a SP to participate	Self-report item	9. Moderate relationship violence	IPSVS Adapted ¹⁰⁸
5. Willing to be seen via telehealth when in-person treatment options aren't available.		10. Veteran has underlying medical condition or a planned medical procedure likely to impair ability to engage in treatment.	
		11. SP screens positive for PTSD	PCL-5
		12. Veteran and/or SP fails to complete baseline survey	

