Criteria for items 3-4 will be assessed through single yes/no self-report items administered to Veterans during telephone screens or on self-reports (IC participants only). Given the emphasis on flexibility, item 4 will require the Veteran to agree to (a) allow a SP to complete study assessments, (b) bring a SP to Session 1, if randomized to family supported PE, and (c) discuss further SP attendance with his/her provider. Variability in SP attendance will be included as a covariate in analyses and examined as a predictor of adherence. Relationship violence will be assessed by telephone from both Veteran and SP-report (item 9), defined as one or more episodes of severe violence in the past year (e.g., kicked or beat up) on the IPSVS Adapted Scale¹⁰⁶. We will exclude Veteran participants if he/she has an underlying medical condition or a medical procedure (item 10) planned that would greatly impair their ability to participate in a weekly psychotherapy (i.e., a severe seizure disorder making weekly attendance difficult or a planned major surgery within a month of beginning treatment). This item will be assessed during the initial phone screening. We will administer a PTSD screen (PCL-, response options adapted to a yes/no format for efficiency of delivery by telephone) to SPs by telephone and exclude SPs who screen positive for PTSD on the PCL-5. SPs and Veterans will be required to complete a baseline survey assessment before they can be randomized to a study arm. Failure to complete the baseline survey will result in study ineligibility (item 11). If a family member is determined to be ineligible due to a positive PTSD screen or failure to complete his/her baseline survey, but the Veteran is otherwise eligible, the Veteran will be contacted by telephone and given the opportunity to designate another family member for participation. The details of the reason their initial SP was ineligible will not be disclosed.

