Regarding relationship violence, when the veteran reports they have been the target of moderate violence from their SP, the study team, under the supervision of the local Site PI, will determine if the violence should be the immediate focus of clinical attention. That is, (1) is the reporter is in danger of harm and, therefore, the focus of clinical attention should be on safety, or (2) would the reporter prefer to focus on IPV rather than PTSD. Importantly, each Site PI is a licensed, clinical psychologist with the appropriate training and expertise to make these

decisions. If the violence should be the focus of immediate clinical attention, then the dyad will be deemed ineligible and provided appropriate referrals. If the violence should not be the focus of clinical attention (e.g., the reporter is not in danger and does not wish to focus on IPV) the reporter may select a different loved one with which to participate in the study.

The new SP will also be screened and subject to the same inclusion/exclusion criteria, including that the new SP cannot be ineligible due to moderate IPV towards the veteran. The original SP will be deemed ineligible. The details of the reason the initial SP was ineligible will not be disclosed. The reporting dyad member(s) will be provided with resources and referrals for IPV (see IPV risk algorithm). Ineligible dyads may be re-evaluated for eligibility when this exclusionary criteria has been resolved (i.e., one year has passed without an episode of severe violence or six months without minor violence).

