Of note, while consent takes place after the initial phone screening, randomization (RCT phase only) does not take place until participants have met inclusion/exclusion criteria. Since we are proposing that consent procedures for SPs be the same regardless of their treatment assignment (consent by phone), we do not need to know randomization when we are recruiting and consenting SPs. Once both members of the dyad have been deemed eligible for the study,

participants will be notified of their randomization when it is time to schedule their (or the Veteran's) first treatment session.

5.4B. Veteran Informed Consent.

After completing the recruitment steps described above, Veterans will participate in informed consent procedures. Veteran participants will participate in informed consent over the telephone with a study staff member. Subjects can meet with a study staff member for in-person informed consent if they prefer. In this case, participants meeting face-to-face for informed consent will be required to sign an official informed consent form instead of having their consent recorded.

Informed consent will be obtained before obtaining any Baseline self-reports (IC and RCT) or Baseline interviews (RCT and up to 10 IC cases). As these Baseline procedures are also necessary for establishing final eligibility (RCT: SCID-5-CT and CAPS-5; IC: PCL-5, PHQ-9, AUDIT, DAST), Veterans will be notified that the baseline procedures are necessary for establishing final eligibility and they may be deemed ineligible for the study after these procedures. For IC participants, those who meet final inclusion/exclusion criteria and remain interested will proceed with treatment (family-supported PE). For RCT participants, those who meet final inclusion/exclusion criteria and remain interested will then be randomly assigned. They will receive notification of their assignment when contacted to schedule their first therapy appointment. Individuals deemed ineligible will be told by telephone and Veterans referred back to their referring providers.

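### The crisis-triage text lets a support person re-enter once stabilized after a partner-violence emergency, without reference to the violence-free periods in section 5.3

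*Combined protocol and SAP*

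**What the plan says.** Section 5.1K.1 (Protection Against Risk) describes what happens in an unusual on-site psychiatric emergency involving a non-Veteran participant, "including threats of or acute risk for IPV, the participant will be triaged within VA facilities". After any transfer to community care, the paragraph closes: "Once stabilized, they will be eligible to enter or re-enter the study". It states no waiting period and no repeat violence screen, and does not refer to the eligibility criteria.

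Section 5.3 sets the violence rules:
- Table 4, criterion 9, excludes "Moderate relationship violence".
- The text below the table takes this from both Veteran and SP report, "defined as one or more episodes of severe violence in the past year".
- When the Veteran reports being the target, the study team under the site investigator decides whether the violence needs immediate clinical attention. If so, the dyad is ineligible. If not, the Veteran may name someone else, and "The original SP will be deemed ineligible".
- "Ineligible dyads may be re-evaluated for eligibility when this exclusionary criteria has been resolved", explained as "one year has passed without an episode of severe violence or six months without minor violence".

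Section 5.4A adds that "randomization (RCT phase only) does not take place until participants have met inclusion/exclusion criteria". Section 5.7 anticipates ending participation when someone becomes ineligible.

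**The concern.** The sentence in 5.1K.1 is a positive statement that the person will be eligible, and the only condition is being stabilized. Section 5.3 offers only the possibility of re-evaluation, and only after a stated violence-free period. A coordinator handling an SP after a violent incident on site could follow either section and be within the protocol.

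This bears on participant safety. In the family arm the SP joins the Veteran in session 1 and is encouraged to attend 2a and 2b, and providers may add further dyadic sessions, including for trauma disclosure (section 5.1D). Re-entry can therefore put the two people involved in the incident back in one session. Section 5.4A makes study contact with SPs in standard PE remote, so an on-site rule falls mainly on SPs who attend sessions.

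**Working it through.** There is no figure to reproduce and no power or error-rate calculation. The check sets the sections side by side.

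**Step 1: what triggers each rule.** The 5.1K.1 sentence is triggered by an on-site psychiatric emergency, with threats of or acute risk for IPV named. It does not distinguish perpetrator from victim, or say that the other party is the enrolled Veteran. Criterion 9 is triggered by a severe episode in the past year. The violence-free periods apply to dyads already found ineligible on that ground.

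**Step 2: apply both rules to each case.**

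| Case | Section 5.1K.1 | Section 5.3 | Result |
|---|---|---|---|
| Emergency without violence between dyad members | Eligible once stabilized | Criterion 9 not engaged | No conflict |
| Threat or acute risk, no episode | Eligible once stabilized | Criterion 9 not met on its face | No direct contradiction |
| Severe episode, dyad not yet randomized | Eligible to enter once stabilized | Excluded; re-evaluation after one year | Wording conflicts, but screening before randomization still controls entry |
| Severe episode, SP already enrolled | Eligible to re-enter once stabilized | Type of episode is exclusionary; re-evaluation after one year | Unreconciled |
| Minor violence only, SP already enrolled | Eligible to re-enter once stabilized | Six-month condition is stated, but minor violence is not in the criterion 9 definition | Unclear |

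The one-year and six-month periods are separate conditions by severity, not the ends of a range.

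**Step 3: does another section settle re-entry?**
- Section 5.4A makes eligibility a condition of randomization. It does not reach an SP already randomized.
- Section 5.7 speaks of becoming ineligible. But section 5.1I.1 ties the violence exclusion to the screening process, and section 5.3 assesses it by telephone screen. Nothing says that an episode after enrolment makes the SP or dyad ineligible.
- Section 5.4C requires repeat baseline assessment only when therapy would start 2 months after baseline. It does not cover return during treatment.
- Section 6.0 makes severe violence on later surveys a reporting matter and sets no participation rule.

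**Step 4: what the difference would mean for an enrolled SP.** If the 5.3 periods were applied after enrolment, the shorter is six months, about 52/2 = 26 weeks. Treatment is planned over 11 to 16 weeks, and section 5.5A.2 puts the latest posttreatment assessment at 24 weeks after session 1. Either period would outlast that window, so the SP would in effect take no further part in treatment. Under 5.1K.1 the SP could return within it if stabilized in time. The choice of section can therefore decide whether the SP returns at all.

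**The case against.** The strongest reply is that a crisis-triage paragraph need not repeat the eligibility criteria. On this reading 5.1K.1 means only that an emergency is not in itself a permanent bar, and everything in 5.3 still applies. Other safeguards support this. Violence is screened from both dyad members, and severe violence on the baseline survey is exclusionary (section 6.0). Providers review violence items for active cases (section 5.1K.1), therapists must report family violence at once (section 6.0), and there are weekly calls with investigators (section 5.1G). Section 5.1K.1 also calls its thresholds minimal and lets sites assess more stringently.

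Much of this stands, and it rules out several stronger readings that a reader might infer:
- That the safety screen can be bypassed. Nothing in 5.1K.1 waives Table 4, and 5.4A protects first entry.
- That every threat or acute risk contradicts 5.3. Criterion 9 is defined by episodes of severe violence.
- That the gap is days against months. No duration for stabilization is given.
- That such events are frequent. Section 5.1K.1 calls them unusual; the expectation of some severe violence in section 6.0 concerns survey reports, not on-site emergencies.
- That outcome collection for an affected dyad is undefined. Section 5.1F keeps participants whose treatment has ended in all assessments, and section 5.6B1 specifies intent to treat, which largely covers it.

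The reply does not dispose of re-entry. The reporting and oversight provisions say who is told and who responds, but none states a condition for return. The only sentence that addresses re-entry after such an emergency is the one in 5.1K.1, and it is unconditional. The site investigator's judgement in 5.3 about danger to the reporter has no counterpart there.

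**Conclusion.** The point holds in a narrow form. For an enrolled SP whose on-site emergency involved an actual violent episode with the Veteran, 5.1K.1 grants re-entry on stabilization, while 5.3 treats a severe episode as exclusionary and withholds even re-evaluation for one year. The conflict is clearest for severe violence. For minor violence it is blurred, because 5.3 labels the exclusion moderate, defines it by severe episodes, and mentions minor violence only in the re-evaluation condition.

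This rests on two readings: that the non-Veteran participant is in practice the SP, and that the episode was between dyad members, which 5.1K.1 does not specify. The affected number cannot be estimated from the documents, and no effect on sample size, power or type I error follows. It is a participant-safety inconsistency, probably rare, that should be corrected because the present text is a stated rule rather than a mere silence.

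**What to change.** Reconcile sections 5.1K.1, 5.3 and 5.7. Make the closing sentence of the 5.1K.1 paragraph expressly subject to whichever section 5.3 rule the sponsor and site investigators decide governs entry and re-entry after a violence-related emergency. State in 5.7 whether violence after enrolment counts as becoming ineligible. While doing so, use one set of severity terms in Table 4, the criterion 9 definition and the re-evaluation condition, so that the cross-reference points to a single rule. No view is offered on which rule is right; that is for the study team.

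The cost is a sentence or two in a protocol amendment, with a matching note in staff training. No change to the design, sample size or analysis is needed.

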
Our protocol parallels that utilized by other investigators at the hub site (i.e., Schertz et al., in preparation). We will employ their algorithm, which includes four phases: (1) Activation, (2) Decision Making, (3) Action, and (4) Documentation (Figure 1). *Activation* is the phase during which concerning risk-related statements are identified (purple boxes in Figure 1). This leads staff to enter the *Decision Making* phase. Decision making includes a series of structured questions with clear decision rules. The flow chart in Figure 1 accounts for the multiple scenarios in which suicidal ideation and behavior may have been encountered within our study. We anticipate that in some circumstances depression or suicidal ideation and behavior will be suspected by research staff but not explicitly endorsed. In this case, staff will initiate the First Tier (2a) of the Decision Making phase (pink boxes in Figure 1), which will use a modification of the Patient Health Questionnaire-2 to assess depression and thoughts of self-harm (Kroenke, Spitzer, & Williams, 2003). When suicidal ideation and behavior is directly endorsed, staff will enter the Second Tier of the Decision Making phase (2b; blue boxes in Figure 1), which will utilize the Columbia-Suicide Severity Rating Scale (C-SSRS) Adult Screener for Primary Care to assign what action staff should perform (Figure 2; Posner et al., 2011). This concise measure includes six questions and can be administered by non-clinicians via telephone or in-person (The Columbia Lighthouse Project, 2016). The Schertz et al. (in preparation) protocol replaced the use of the double barreled final PHQ-9 item (In the past two weeks, have you been having any thoughts that you would be better off dead, or of hurting yourself?) with a modified item adapted from the Ask Suicide-Screening Questions (ASQ) "In the past two weeks, have you been having thoughts about killing yourself?" due to concerns that participants may have trouble responding to the double-barreled PHQ-9 item and that the PHQ-9 item does not directly ask about active thoughts of suicide. The ASQ item was selected due to its direct, action-oriented wording. The *Action* phase (3; green boxes in Figure 1) will use responses from the C-SSRS to stratify patients into low-concern or high-concern categories to aid immediate decisions around what response staff should provide. Staff response will be informed by proximity to the patient, if the participant has a VA MH provider, resources available at the study site, and level of concern. Responses range from providing resources for support, referral for assessment, immediate evaluation by a mental health professional, phone transfer to a crisis hotline (e.g., the National Suicide Prevention Lifeline), admission to the emergency department, to contacting 911 to coordinate a welfare visit (Draper et al., 2015). Of note, all responses involve notifying the participants' VA MH provider of this protocol, when one exists. The *Documentation* phase is described in greater detail below.

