
When staff interact with participants over the phone and wish to transfer a participant to the National Suicide Prevention hotline, it is possible, albeit unlikely, that the patient will decline the transfer or hang up. This refusal to be transferred does not necessarily mean the patient is immediate danger of suicide. We consulted with the hub site's Suicide Prevention Program Coordinator on how to respond in this scenario ([name]). [name] recommended the following: (1) If the staff member is able to determine that the patient is not in immediate danger for suicide (e.g., "Are you certain you are safe today?"), then staff member should express his/her care and concern, encourage help seeking, provide the patient with the national suicide hotline number and local MH phone number(s), and respect his/her wishes not to be transferred. (2) If the staff member is concerned the participant may be in immediate danger, he/she will contact local police and initiate a well-check if the participant is unwilling to be transferred. (3) If the staff member does not have enough information to determine if the participant is in immediate danger, he/she will immediately consult with the site PI (each of whom are clinical psychologists) or another MH provider among the study staff, whomever the staff member is able to reach first. This is most likely under scenarios in which the participant hangs up on the staff member and failed to respond to the staff members efforts to call him/her back.

The final phase of our suicide management protocol is *Documentation*. Staff will report use of the suicide management protocol within the same day to the site's study coordinator and site principal investigator. For veteran participants who receive their care at that study site, use of the protocol will be documented in the

patient's electronic medical record. This will also be done for VA patients not enrolled in the study (e.g., when interactions happened during recruitment). If the participant has a VA mental health provider, this individual will be notified by co-signing the provider on the CPRS note (their MH provider, or if no MH provider their PCP) using the use the CPRS Action "Identify Additional Signers". Lastly, this will be recorded in study records as an adverse event and in an excel document for the study that documents all the steps taken in response to the participant's expressed suicidal ideation.

Figure 1. Suicide Management Protocol

[figure not shown]

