Reports of risk on study surveys. All surveys will be screened within 2 business days of receipt by study staff. This will ensure that surveys are typically screened within 48 hours of receipt by a study staff, barring holidays and weekends (e.g., staff has until Tuesday to screen a survey received on Friday). Staff will read any text written into the survey for any risk-related concerns, as well as review responses to the adapted Linehan BRTC SI screen items that directly assess suicidal ideation. Staff will be carefully trained about the importance of opening surveys promptly and entering receipt of each survey into the study tracking application. Auditing will be performed quarterly to ensure that the staff member reviewed the participants responses on Linehan BRTC SI screen items and intervened appropriately when the final item response was greater than "5".

If any psychiatric emergency is reported on surveys (i.e., expression of risk for suicide or homicide) or a response of greater than "5" on Linehan BRTC SI screen items, the participant's VA Mental Health Provider will be notified using phone, skype, and pager. If the participant does not have a VA Mental Health Provider or their VA Mental Health Provider is unavailable (we are not able to reach the provider within the same business day), a study designated MH provider would do the necessary outreach. There are a number of licensed MH providers on the study team. Some are clinically privileged and others are not clinically privileged (e.g., Research Service employees). When providers are not privileged, we propose they will utilize the C-SSRS screener as outlined in the study protocol (see "Suicide Management Protocol"). When providers are privileged, we propose they use either the C-SSRS screener protocol or a more stringent approach to suicide risk assessment that is consistent with VA guidelines.

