6.0 Reporting

We will follow the VA Central IRB Table of Reporting Requirements for all issues that must be reported (i.e. summary of adverse events, unexpected problems and any actions or changes with respect to the protocol).

Adverse events (AE) include any untoward medical occurrence in a patient or clinical investigation subject administered an intervention and which does not necessarily have a causal relationship with this treatment. We will collect the following safety information (adverse events) that occurred within 7 days leading up to the final assessment.

1. Suicide attempts
2. Hospitalizations for mental health
3. Episodes of family violence

Therapists will be instructed to notify study staff immediately when such events occur during treatment delivery. Staff will report directly to the local site PI regarding any events. Counselors will also meet regularly by phone for case consultation with a study investigator, where the occurrence of any of these events will be further discussed and tracked. Questions regarding the occurrence of each of these three events will be included in posttreatment assessments. Data obtained from participants will be reviewed for safety concerns. In the case of problems, the staff will discuss this with the appropriate site PI.

Of note, survey reports of IPV on posttreatment and follow-up surveys will be reported when respondents endorse items consistent with severe violence. This includes the following: (1) hit my partner with a fist or something hard, (2) kicked my partner, (3) slammed my partner against something, (4) beat my partner, (5) burned my partner on purpose, (6) tried to hurt my partner by choking or suffocating him/her, or (7) used a knife or gun on my partner. Examples of serious adverse effects, according to the FDA, include death, life-threatening adverse events, suicide attempts, and hospitalization. Consequently, endorsement of items 6 or 7 will be considered a SAE. Given the population, some incidents of severe IPV are expected. Reports of severe IPV on baseline surveys are part of our exclusionary criteria (see inclusions/exclusions). Thus, severe IPV in reported in baseline surveys will not be reported as adverse events.

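### Section 5.1K.1 makes use of the suicide management protocol an adverse event, 6.0 does not list it, and the survey rule leaves some reports unassigned, so the ideation count may depend on who responds

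*Combined protocol and SAP*

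**What the plan says.** Three parts of the plan bear on this.

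- **5.1K.1, Suicide Management Protocol, Documentation phase.** The duty starts from use of the protocol: "Staff will report use of the suicide management protocol within the same day to the site's study coordinator and site principal investigator". After the medical-record note and notification of the provider, the paragraph ends: "Lastly, this will be recorded in study records as an adverse event". No time window is given.
- **6.0 Reporting.** The general definition is broad: "Adverse events (AE) include any untoward medical occurrence in a patient or clinical investigation subject administered an intervention". The collection statement is narrower: "We will collect the following safety information (adverse events) that occurred within 7 days leading up to the final assessment". The list that follows is suicide attempts, mental health hospitalizations and family violence. Therapists are told to notify staff of those events, and "Questions regarding the occurrence of each of these three events will be included in posttreatment assessments".
- **5.1K.1, Reports of risk on study surveys.** A survey expressing risk, or a response above 5 on the suicidal-ideation screen items, goes first to the participant's VA mental health provider. A study-designated clinician steps in under this condition: "If the participant does not have a VA Mental Health Provider or their VA Mental Health Provider is unavailable". A study clinician who is not clinically privileged uses the C-SSRS screener from the suicide management protocol. For privileged clinicians, "we propose they use either the C-SSRS screener protocol or a more stringent approach to suicide risk assessment".

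**The concern.** In 5.1K.1 the adverse event is attached to a response (the protocol was used) and not to what happened to the participant. Section 6.0 works from named events and does not name this one. Two coordinators, each following one section, could keep different adverse event files on the same participants.

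The survey rule adds to this. Its only link to the suicide management protocol, and so to the adverse event step, lies in the fallback branch. The same answer on the same survey may then be recorded or not according to whether a provider existed, was reached that day, or chose a different assessment. The DSMB receives participant-safety reports at least annually (5.1M). A count that partly reflects staffing and reachability is hard to interpret there, and harder still to compare between arms.

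**Working it through.** The plan gives no event rate or adverse event count to reproduce, so the check sets the texts side by side.

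**1. Which route brings ideation into the adverse event file?** Under 5.1K.1, protocol use does, at any time. Under 6.0, the solicited list has three entries and a 7-day window before the final assessment. Therapist notification and the posttreatment questions refer back to those three. Reports of severe partner violence on posttreatment and follow-up surveys are added. The general review of participant data for safety concerns names neither ideation nor protocol use. Ideation without an attempt or hospitalization therefore has an explicit route in 5.1K.1 and none in 6.0.

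**2. Follow one survey response above 5 through the survey rule.**

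- (a) Own VA provider reached the same business day: the provider is notified. No C-SSRS, no reference to the suicide management protocol and no adverse event step is mentioned.
- (b) Fallback, study clinician not privileged: C-SSRS screener under the suicide management protocol, hence an adverse event.
- (c) Fallback, privileged clinician who chooses the C-SSRS protocol: an adverse event.
- (d) Fallback, privileged clinician who chooses another approach: no adverse event step is stated.

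Recording is explicit in (b) and (c), and unstated in (a) and (d).

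**3. What range does that leave?** Let N be the number of triggering reports, p the share handled by the own provider, and q the share of the remainder handled by another approach. Counting only the explicit branches:

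recorded events = N × (1 − p) × (1 − q)

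With p = 0 and q = 0 this is N. With p = 1 or q = 1 it is 0. If (a) and (d) are also meant to be recorded, the count is N whatever p and q are. The documents give none of N, p or q, so no narrower range can be supported.

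**4. When does recording start?** The suicide management protocol covers screening and consent contacts, and the medical-record note extends to VA patients not enrolled. That extension follows the medical-record sentence, not the adverse event sentence. Section 6.0 defines adverse events in subjects administered an intervention. The two do not settle whether an activation before randomization counts.

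**5. What is the survey trigger?** The outreach sentence refers to a response above 5 on the screen items. The quarterly audit sentence refers to the final item being above 5. These are different rules if an earlier item can exceed 5 when the final one does not.

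**The case against.** The strongest reply is that the sections can be read as additive. The definition in 6.0 is broad and nothing in it excludes an event recorded under 5.1K.1; the three listed events may simply be the solicited ones. This stands: a reader might infer that 6.0 rules ideation out, and it does not. It only fails to name it.

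A reader might also infer that a survey report becomes an adverse event only when a study clinician responds. The documents do not support that. The survey rule says nothing about adverse events on any branch. The suicide management protocol treats notifying the VA provider as part of every response, so branch (a) could itself count as protocol use. The text says of the flow chart: "The flow chart in Figure 1 accounts for the multiple scenarios in which suicidal ideation and behavior may have been encountered within our study". That figure is not reproduced in the copy reviewed, so the question cannot be closed. What remains is that the written rule does not tell staff which reading applies.

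A third tempting inference is that better retention in family supported PE would lower its recorded ideation events, because retained Veterans have a provider to page. No passage says that Veterans who stop PE lack a reachable provider. All must be enrolled in VHA care (Table 4), and those who finish treatment are referred to a VA team (5.1D). Study therapists are themselves study staff (5.1I.1), so the split between own provider and study clinician is not clean. More therapy contact could equally raise detection. The direction is unknown.

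It is also fair that section 5.6 plans no between-arm adverse event analysis, so no planned efficacy result is affected.

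**Conclusion.** The point holds as a defect in the recording rule. Section 5.1K.1 ties an adverse event to use of the suicide management protocol, 6.0 does not list ideation or protocol use among what it collects, and the survey rule is silent on reports handled by the participant's own provider or by another approach. The ideation count may therefore depend on who responds. Whether activations before randomization count is also open.

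The size cannot be estimated. The 0-to-N range describes what the wording permits under a literal reading; it does not forecast what happened. No direction of difference between arms can be claimed. The conclusion rests on the text as published, without the flow chart. If the chart treats every triggering survey report as protocol use, the dependence on responder falls away for those reports, but the mismatch with 6.0 remains.

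**What to change.** Reconcile 5.1K.1 and 6.0 with one event-based rule. The change concerns recording only and leaves the clinical response as it is.

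- After randomization, record as suicidal ideation every survey report that meets the survey rule's existing suicide-related trigger, whoever responds and by whatever approach. Reconcile the two wordings of that trigger (any screen item or the final item).
- Use this as the count comparable by arm in DSMB reports. It suits that purpose because the RCT survey schedule is stated without distinction by arm (5.1I.2, 5.5A.2). Show the number of surveys returned in each arm beside it, since return may itself differ.
- Log other protocol activations separately by what was found: endorsed ideation; positive answers to C-SSRS items 6 and 6a as behavior; and activations with no endorsed ideation as such. The protocol's first tier can be activated on suspicion alone, so the last group should not be labeled ideation.
- Keep suicide attempts as their own event.
- Log activations before randomization separately.
- State whether support persons are counted.

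The cost is wording in two sections, one added event category and minor logging work. Surveys are already screened within 2 business days of receipt and audited quarterly, so the triggering data are in hand. The downside is a higher recorded adverse event count.
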